General: Tissue selectivity is achieved by a proprietary knowledge of ultrasound parameters ensuring specific destruction of the fat cells only within the target area. All other types of tissue, such as blood vessels, muscles and peripheral nerves remain intact. There are no thermal effects. Fat cell destruction is achieved by ultrasound-induced mechanical effects during a very short exposure time.

The UltraShape Power system comprised of two main parts:

- The Main console
- Transducer

 Syneron Medical Ltd. Confidential	Clinical Study to Evaluate the Safety and Efficacy of the UltraShape Power Device Using the U-Sculpt Power Transducer for Abdominal Fat and Circumference Reduction			
	Protocol #	DHF21621	Rev. Date	April 05, 2016

Main Console

The Pulser

The main console contains: the Pulser, Touch Screen, PC, Cooling System, Power supply Module and Video Camera. The main console hardware and software enable operation of the Transducer Unit.

The Pulser is responsible for producing high power electrical signals for feeding the Transducer Unit, with the ability to control operating frequencies, burst length, duty cycle and on-line output power. The Pulser has communication interfaces with the PC, the Power Supply Module (PSM), the Distributer Board (DSB), the Transducer and the cooling system. The Pulser is comprised of a CPU unit and Pulse generator. The Pulser uses transducer-unique parameters and "Power Level" (high \ medium \ low) selected by the user to send the relevant electric signal to the transducer.

Touch Screen and PC

The operator interfaces with the UltraShape Power system using its Touch Screen.

The Touch Screen interface allows the user to command and control the system using dedicated software. The Touch Screen interfaces with the Pulser, the camera and external USB. The Touch Screen operates the system's tracking system that uses a video camera in order to monitor the position of the transducer over the patient's body. The System database is managed by the Touch Screen.

Cooling system

Inside the Transducer there is a cooling element (TEC). The cooling system evacuates heat from the hot side of the TEC, by circulating water into the system's radiator.

Power Supply Module

The Power Supply Module (PMS) provides the input power to the system sub-units. The Power Supply Module receives external AC voltage and converts it into DC: Low Voltage and High Voltage. The PSM is controlled by the Pulser and the DSB.

Video Camera

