Figure 9: Patient positioning during circumference measurements (A) and measuring device position around the abdomen (B)

7. The measurement device should be activated at a constant tension to achieve an exact measurement of the circumference (use measurement device supplied by Syneron only).
8. In order to minimize measurement inaccuracies originating from human error, it is recommended that, whenever possible, the same operator re-measures the patient at approximately at the same hour of day (± 3 hours).
9. Patients should be under fasting for at least 3 hours prior to circumference measurement.

Treatment Procedure

Subjects will receive treatments with UltraShape Power device utilizing the U-Sculpt Power Transducer on the anterior abdomen.

Prior to each treatment measurements of weight, fat thickness (both by Ultrasound and Caliper), and abdominal circumference will be done according to the references from the enrollment visit (Baseline/ prior to Tx.1). Only patients who are eligible for treatment will be allowed to undergo the UltraShape Power procedure.

Enrolled subjects will undergo 3 successive bi-weekly (2 weeks interval) treatments (Tx.1, Tx.2 and Tx.3). Additional three (3) visits in the clinic will be occurred to follow-up the abdominal fat and circumference reduction at visits 4, 5 and 6 (4 weeks, 8 weeks and 12 weeks following last treatment).

 Syneron Medical Ltd. Confidential	Clinical Study to Evaluate the Safety and Efficacy of the UltraShape Power Device Using the U-Sculpt Power Transducer for Abdominal Fat and Circumference Reduction			
	Protocol #	DHF21621	Rev. Date	April 05, 2016

UltraShape Power Treatment Procedure

The subject abdomen will be gathered using reusable straps (supplied by Syneron Medical), to gather the fat area for treatment according to the instruction written in the User Manual.

According to size of the treatment area, the UltraShape Power device will determine the total number of FTZs to be delivered during treatment. While the recommended minimal number of ultrasound FTZs to be delivered per subject at a whole single treatment will be defined / determined by the system according to the subject physical characteristic and treated area size. Prior to admitting the FTZs (pulses) Parker acoustic gel will be applied and on the treated area and used as a coupler agent between the ultrasonic U-Sculpt Power Transducer and the skin surface.

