An adverse event (AE) is any adverse change in health or side effect that occurs in a study participant during their participation in the study.

Anticipated Adverse Effects

Following treatment with the UltraShape Power the following local adverse effects could occur (anticipated):

- Purpura
- Blister
- Bruising
- Bullae
- Erosion
- soreness
- First degree burn
- Second degree burn

An adverse event (AE) is any undesired clinical occurrence in a study subject as indicated by signs, symptoms, illnesses, events that develop or worsen in severity in association with the study when deemed by the Investigator to be related to use of the device or study procedures. The Investigator will document all adverse signs and symptoms regardless of severity or frequency that are either volunteered by subjects or observed during the course of the study that are related to the device. The Investigator will also record adverse experiences of subjects resulting from concurrent illnesses, reactions to concurrent medications, or progression of disease states that the Investigator deems related to the device. Included in the description will be the nature of the sign or symptom, the date of onset, whether the event was serious, the severity, the relationship to study procedures or investigational device, the action taken, the

 Syneron Medical Ltd. Confidential	Clinical Study to Evaluate the Safety and Efficacy of the UltraShape Power Device Using the U-Sculpt Power Transducer for Abdominal Fat and Circumference Reduction			
	Protocol #	DHF21621	Rev. Date	April 05, 2016

date of resolution, and the outcome. The Principal Investigator will determine the relationship of the adverse device effect to the investigational device.

Unanticipated Adverse Device Effects

For device studies, part 21 CFR 812.3(s) uses the term unanticipated adverse device effect which is defined as any serious adverse effect on health or safety or any life-threatening problem or death caused by, or associated with the device, if that effect, problem, or death was not previously identified in nature, severity, or degree of incidence in the investigational plan or application (including a supplementary plan or application), or any other unanticipated serious problem associated with a device that relates to the rights, safety, or welfare of subjects.

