Significant device failure may constitute an adverse event if an undesirable experience occurs. This definition includes any event resulting from insufficiencies or inadequacies in the instructions for use or the deployment of the device, or any event that is a result of a user error.

All unanticipated adverse effects will be graded as follows:

Mild: Sign or symptom, usually transient, non-life-threatening requiring no special treatment and generally not interfering with usual activities.

Moderate: Sign or symptom, non-life-threatening which may be ameliorated by simple therapeutic measures, and may interfere with usual activity.

Major: Sign or symptom that is intense or debilitating but non-life-threatening and that interferes with usual activities. Recovery is usually aided by therapeutic measures and the discontinuation of the study device may be required.

Severe: Any untoward medical occurrence that at any time results in death or life-threatening illness, resulting in persistent or significant disability/incapacity.

The relationship of the adverse effect to the study is defined as follows:

Probable: An adverse event has a strong temporal relationship to study device, and another etiology is unlikely or significantly less likely.

Possible: An adverse event has a strong temporal relationship to the study device, and an alternative etiology is equally or less likely compared to the potential relationship to study device.

Probably not: An adverse event has little or no temporal relationship to the study device and/or a more likely alternative etiology exists.

Not related: An adverse event has no temporal relationship to study device or has a much more likely alternative etiology.

 Syneron Medical Ltd. Confidential	Clinical Study to Evaluate the Safety and Efficacy of the UltraShape Power Device Using the U-Sculpt Power Transducer for Abdominal Fat and Circumference Reduction			
	Protocol #	DHF21621	Rev. Date	April 05, 2016

Reporting Adverse Events (AE) and Serious Adverse Events (SAE)

Anticipated Adverse Events: Anticipated adverse events in this study include Purpura, blistering, bruising, bullae, erosion, soreness and burn. If an unanticipated adverse event occurs at any time during or after the use of the UltraShape Power device, the Investigator must report it to Syneron.

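### The only causality scale rates adverse events against the study device alone, although the plan asks for the relationship to study procedures as well, so harm put down to strapping could be rated unrelated

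*Combined protocol and SAP*

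**What the plan says.** All references are to the combined protocol and SAP.

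- **Adverse event definition** (Adverse Events, under Anticipated Adverse Effects). An event qualifies "when deemed by the Investigator to be related to use of the device or study procedures". The description of each event must include "the relationship to study procedures or investigational device".
- **Device-only sentences** (same paragraph). The investigator is told to document signs and symptoms that are related to the device. The paragraph ends: "The Principal Investigator will determine the relationship of the adverse device effect to the investigational device".
- **Table 2, Safety row.** The attribute to be captured is relation to treatment.
- **Causality scale** (Unanticipated Adverse Device Effects). The lead-in is wide: "The relationship of the adverse effect to the study is defined as follows". The categories are narrow. The first is "Probable: An adverse event has a strong temporal relationship to study device, and another etiology is unlikely or significantly less likely" and the last is "Not related: An adverse event has no temporal relationship to study device or has a much more likely alternative etiology". *Possible* and *Probably not*, between them, are also worded against the study device.
- **Strapping** (UltraShape Power Treatment Procedure). "The subject abdomen will be gathered using reusable straps (supplied by Syneron Medical), to gather the fat area for treatment".
- **What the device is** (Device Descriptions). "The UltraShape Power system comprised of two main parts": the main console and the transducer. The straps, gel and caliper come later, in the list of accessories needed for treatment.

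**The concern.** The plan asks for a judgment that its scale cannot record. An investigator who thinks the strap caused a bruise has to answer a question about the device, and the scale treats any more likely other cause as a reason to move the event towards unrelated. Nothing says that a cause belonging to the study procedure does not count as such an alternative.

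No subject is to be treated without strapping, and the Safety paragraph under Data Analysis sets out to evaluate the safety of the device procedure. The informative classification is therefore whether the whole treatment caused the event. With one arm, no comparison group would show that events had been attributed elsewhere. With up to ten sites, investigators may differ on whether a strap is part of the device. Where the wording does move an event, it moves it away from the device.

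**Working it through.** No sample size, rate or interval is involved, so the check sets the passages side by side.

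**Step 1. What the scale covers.** Of the four category definitions, 4 of 4 refer to the study device and 0 of 4 mention study procedures. No second scale for procedures is given.

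**Step 2. Which criterion decides.** *Probably not* joins weak timing and a more likely other cause with and/or. *Not related* joins absent timing and a much more likely other cause with or. In both, the other cause is enough by itself. An event that appears right after a session, with perfect timing for the device, can still land in either category.

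**Step 3. Apply it to a bruise seen straight after a session.**

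| Investigator's view | Category on the literal wording |
|---|---|
| Strap counts as part of the device; no other cause likely | *Probable* |
| Strap is outside the device; strap significantly less likely than ultrasound | *Probable* |
| Strap is outside the device; the two equally likely | *Possible* |
| Strap is outside the device; strap more likely | *Probably not* |
| Strap is outside the device; strap much more likely | *Not related* |

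The last two rows are the problem. They need two judgments: that the strap is not part of the device, and that it is the more likely cause. The device description gives grounds for the first by naming only the console and transducer as main parts. Bruising, purpura and soreness, all on the anticipated list, are plausible effects of compression, so the second is not far-fetched.

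**Step 4. Other procedures.** Caliper and tape measurements are also taken at the 4-, 8- and 12-week follow-up visits, when no treatment is given. Harm from these has no category that fits, even if the strap is accepted as part of the device.

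**Step 5. Does it change what is counted?** The Primary Safety Endpoint counts any adverse event recorded during the study, by severity and type, with no relatedness filter. A strap bruise that is recorded is therefore counted whatever its causality rating. The count is at risk only through the sentence limiting documentation to device-related signs. A site that follows that sentence, rather than the wider definition in the same paragraph, could leave out an event that it attributes to the strap.

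**The case against.** The strongest reply is that the mismatch does little harm. The primary safety endpoint takes in every recorded event, and the plan specifies no device-related rate. Post Treatment Procedures has every visible and palpable immediate response recorded over the whole treatment area, whatever its cause. Table 2 speaks of relation to treatment, and strapping is part of the treatment procedure. The scale's own lead-in refers to the study. An investigator thus has textual grounds for rating a strap bruise as related. A list of two main parts does not exclude accessories, and the sponsor supplies the straps.

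Much of this stands. A reader might infer that strap harm *is* rated unrelated, or that the primary safety endpoint is biased in the device's favour. The documents support neither: the rating depends on the two judgments in step 3, and the endpoint is not filtered by causality. What does not stand is that the wider statements cure the scale. They show what the plan wants recorded, but the category definitions are what the investigator applies, and these name only the device.

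A second reply is that the scale sits under a heading on unanticipated effects, while bruising, purpura and soreness are anticipated. The severity grading is expressly limited to unanticipated effects, but the causality lead-in is not, and no other causality scale is offered. If it were limited, anticipated events would have no causality definitions at all.

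A third is that a sentence in the same section brings in events arising from deployment of the device or from user error. That widens what counts as an adverse event and leaves the four categories unchanged.

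**Conclusion.** The inconsistency is real and should be corrected. The plan requires causality against study procedures or device, and its only scale defines causality against the device. Events judged more likely due to strapping or another study procedure *could* be rated *Probably not* or *Not related*. The consequence is a relatedness classification that may differ between sites and understate harm from the treatment as a whole. The event count is affected only where the narrower documentation sentence is followed.

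The size cannot be estimated. The documents report no frequency of strap or procedure harm and no split of bruising between strap and ultrasound, so any figure for misclassified events, or for a lowered device-related rate, would be invented. The case report form is not among the documents and might already separate device from procedure. The conclusion rests on the protocol wording alone.

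**What to change.** 1. In all four categories, replace the reference to the study device with *study device or any study procedure (including strapping)*.
2. State that a study procedure does not count as an alternative etiology.
3. Align the two device-only sentences under Anticipated Adverse Effects, the one limiting what is documented and the one on the investigator's determination, with the wider definition in the same paragraph.
4. Summarise related events as device or procedure combined.

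A field for the suspected component (ultrasound, strap, gel, other) is optional. Strap and ultrasound effects occur together and often cannot be told apart, so it may record guesses.

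The cost is protocol wording and matching text on the adverse event form. The downside for the sponsor is that the reported treatment-related count may be slightly less favourable.

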APPENDIX I – STUDY SUMMERY

Table 3 - Study Schematics

	Screen / Baseline* Tx.1	Tx.2 ±5 days	Tx.3 ±5 days	4 weeks Follow-Up (4wk FU) ±7 days	8 weeks Follow-Up (8wk FU) ±7 days	12 weeks Follow-Up (12wk FU) ±7 days
Informed Consent Process	X					
Eligibility Screening & Medical History	X					
PERFORM BEFORE TREATMENT	Photography	X	X	X	X	X
	Height	X				
	Weight (BMI calculation)	X	X	X	X	X
	Marking of the Treatment Areas	X	X	X		
	Transplant Preparation	X				
	Fat Thickness Ultrasound Measurement (Prior Strapping)	X		X	X	X
	Fat Thickness Caliper Measurement (Prior Strapping)	X	X	X	X	X
	Fat Thickness Caliper Measurement (Prior Strapping)	X	X	X		
	Circumference Measurements	X	X	X	X	X
Treatment	X	X	X			
Subject Pain Assessment	X	X	X			
Safety Monitoring	X	X	X	X	X	X
Subject Questionnaire				X	X	X
Investigator Questionnaire				X	X	X
Urine Pregnancy Test	X	X	X			X
End of Participation (Termination)						X

APPENDIX II - SCALES

Table 4 - Post Treatment Side Effect Severity Scale

(0) Absent / None	
(1) Mild	
(2) Moderate	
(3) Severe	

Table 5 – Global Aesthetic Improvement (GAI) Scale

(0) No change	
(1) Slight improvement	
(2) Moderate improvement	
(3) Significant improvement	

[figure not shown]
Table 6 – Satisfaction Scale

(0) Dissatisfied	
(1) No Opinion	
(2) Satisfied	
(3) Very Satisfied	

SYNERON CANDELA Syneron Medical Ltd. Confidential	Clinical Study to Evaluate the Safety and Efficacy of the UltraShape Power Device Using the U-Sculpt Power Transducer for Abdominal Fat and Circumference Reduction			
	Protocol #	DHF21621	Rev. Date	April 05, 2016

APPENDIX III - PAIN ASSESSMENT

Immediately after treatment the subject will be asked to rate treatment related pain. Pain will be assessed post treatment based on the Numerical Scale Response (NSR). The subject will be presented a scale (below) with words along a horizontal line and asked to make a mark along the scale to rate their pain from no pain to worst possible pain. A number will be derived by the research staff by measuring up to the point the subject has indicated versus the entire line.

SYNERON CANDELA Syneron Medical Ltd. Confidential	Clinical Study to Evaluate the Safety and Efficacy of the UltraShape Power Device Using the U-Sculpt Power Transducer for Abdominal Fat and Circumference Reduction			
	Protocol #	DHF21621	Rev. Date	April 05, 2016

APPENDIX IV - PHOTOGRAPHY

At each of the specified time points; photographs of the treated areas should be taken by investigator or their designee.

- Photographs should be taken in a private room or area of the clinic under controlled conditions, including the distance from the camera to the subject, height of the camera, background, camera positioning, subject's positioning and lighting in order to achieve high-quality before & after sets.
- Consistent lighting- Lighting should be projected from about 45° angle in order to emphasize the body appearance.
- It is important to keep a constant distance between the subject's feet (use "sticky feet" or another way of marking) in order to properly present the effect of the treatment. The recommended distance between the feet is ~20 cm, but the main point is not to make this distance too small, so the thighs touch each other, or too large.
- The disposable underwear should be used for all photographs of all of the anatomical areas at all time points.
- For consistency purposes, the same person should ideally take all study photographs, especially per area and subject.
- The digital files should follow a consistent standard naming scheme containing subject initials and study ID #, visit or visit date.

Specific photography details:

Abdomen:

Three photographs should be taken at each specified time point

- Front
- 45° from the right side
- 90° from the right side
- 45° from the left side
- 90° from the left side

The subject's arms should remain out of the way; it is best to either cross them over each other in front of the chest or hold them up at a 90° angle to the body, ensuring that they do not rest on the chest or touch the body and that they do not cast a shadow in the photograph.

 Syneron Medical Ltd. Confidential	Clinical Study to Evaluate the Safety and Efficacy of the UltraShape Power Device Using the U-Sculpt Power Transducer for Abdominal Fat and Circumference Reduction			
	Protocol #	DHF21621	Rev. Date	April 05, 2016

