Assure repeatable marking of treatment area at each treatment visit

STUDY DESIGN OVERVIEW

This study is a prospective, baseline controlled, multi-center, one arm clinical study showing the performance and safety of the UltraShape Power treatment for abdominal non-invasive fat and circumference reduction.

Up to 120 Healthy subjects in up to 10 investigational sites will be enrolled in this study. All subjects will undergo an assessment of their general health. During the treatment period, subject’s fat thickness and circumference will be measured and three successive bi-weekly (two weeks interval) treatments will be performed.

The study subjects will undergo treatments with UltraShape Power device utilizing the U-Sculpt Power Transducer.

During the follow-up period visit will be conducted as follow: 4 weeks (4wk FU), 8 weeks (8wk FU) and 12 weeks (12wk FU) post last treatment (Tx.3). Subject’s fat thickness will be measured in two different methods (Caliper & Ultrasound) and fat reduction will be assessed at each post baseline visit. Circumference will be measured in 3 measurements heights and circumference reduction will be assessed at each post baseline visit. Additionally, investigator and subject questionnaires will be completed. Finally, photography will be performed under visible light conditions of the front, right, left and back view. Most of the assessments will occur at each of the visits to the clinic.

SUTDY OBJECTIVE

The objective of this trial is to evaluate the safety and efficacy of the UltraShape Power device utilizing the U-Sculpt Power Transducer for abdominal non-invasive fat and circumference reduction

Primary Objective

Statistically significant abdominal fat reduction as measured by Ultrasound device post UltraShape Power treatments at 12 weeks follow-up (12wk FU) versus baseline.

 Syneron Medical Ltd. Confidential	Clinical Study to Evaluate the Safety and Efficacy of the UltraShape Power Device Using the U-Sculpt Power Transducer for Abdominal Fat and Circumference Reduction			
	Protocol #	DHF21621	Rev. Date	April 05, 2016

Primary Safety Objective

1. Evaluate the safety of the treatment with the UltraShape Power device utilizing the U-Sculpt Power Transducer during all study.
2. Comfort level during treatment:
Comfort assessment will be performed independently by the subject himself using NSR scale; the subjects will answer this questionnaire after each treatment (Tx.1, Tx.2 and Tx.3).

Secondary Objectives

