1. Statistically significant abdominal fat reduction post UltraShape Power treatments as measured by Ultrasound device at Pre Tx.3, 4 weeks, and 8 weeks follow-up (4wk FU and 8wk FU) versus baseline.
2. Statistically significant abdominal fat reduction post UltraShape Power treatments as measured by calibrated Caliper at Pre Tx.2, Pre Tx.3, 4 weeks, 8 weeks and 12 weeks follow-up (4wk FU, 8wk FU and 12wk FU) versus baseline.
3. Statistically significant abdominal circumference reduction post UltraShape Power treatment/s at Pre Tx.2, Pre Tx.3, 4 weeks, 8 weeks and 12 weeks follow-up (4wk FU, 8wk FU and 12wk FU) versus baseline.
4. Investigator satisfaction:
Satisfaction assessment will be performed by the study investigator using a pre-defined scale questionnaire. The investigator will answer this questionnaire at each follow-up visit (4wk FU, 8wk FU and 12wk FU).
5. Subject improvement and satisfaction:
Improvement and satisfaction assessment will be performed independently by the subject himself using a pre-defined scale questionnaire. The subjects will answer this questionnaire at each follow-up visit (4wk FU, 8wk FU and 12wk FU).

Primary and Secondary Efficacy Endpoint

Primary and secondary objectives will be measured using the next efficacy endpoints:

1. Fat thickness measurements using Ultrasound device
2. Fat thickness measurements using calibrated Caliper
3. Circumference measurements of the abdominal area using Measuring Tape
4. Investigator satisfaction using a pre-defined scale
5. Subject improvement and satisfaction using a pre-defined scale
6. Photography

 Syneron Medical Ltd. Confidential	Clinical Study to Evaluate the Safety and Efficacy of the UltraShape Power Device Using the U-Sculpt Power Transducer for Abdominal Fat and Circumference Reduction			
	Protocol #	DHF21621	Rev. Date	April 05, 2016

Primary Safety Endpoint

The number, severity and type of any adverse event recorded throughout the study and post treatment (discomfort (pain), immediate and delayed response).

1. Occurrence of expected post treatment immediate response including erythema and edema and during all study period based on predefined scale (Table 4).
2. Number, severity and type of any adverse event recorded throughout the course of the study.

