All data will be recorded on site source documents and transcribed onto Case Report Forms (CRFs). The site will be monitored by Syneron staff or designees to assure adherence to the clinical trial requirements, subject safety, protocol procedures, and for data accuracy. The Case Report Forms and images will be reviewed and retrieved during the monitoring visit. All source documentation will remain in the subject's files at the site.

Review and Analysis of all data collected will be conducted by the Sponsor or designee as described for this protocol with the following data:

Demography and Baseline Measurements

Demographic and baseline/screening measurements (e.g., weight, height and digital images) will be collected and descriptively presented.

Treatment Visit

Skin assessment by the PI, photographs of the treated region, and pain scores will be collected used to document any adverse events to assess the device performance.

Follow-up Visit Measurements

Follow-up measurements for weight, circumference and digital images will be used for comparative measurements with their respective measurement at baseline. Primary endpoints will be evaluated 12 weeks post last treatment (Tx.3). Secondary endpoints may be evaluated at all visits.

 Syneron Medical Ltd. Confidential	Clinical Study to Evaluate the Safety and Efficacy of the UltraShape Power Device Using the U-Sculpt Power Transducer for Abdominal Fat and Circumference Reduction			
	Protocol #	DHF21621	Rev. Date	April 05, 2016

Safety

Safety of device procedure will be evaluated through skin assessments by the PI and research staff. The occurrence and severity of all complications from the start of the study will be recorded.

Protocol Revisions and/or Deviations

With the exception of emergency situations, no changes or deviations in the conduct of this protocol will be permitted without the prior approval of the sponsor.

The IRB/IEC that granted original approval for the study must be notified of all changes in the protocol, and will approve any change or deviation that may increase risk to the subject, and/or that may adversely affect the rights of the subject or validity of the investigation.

In the event of an emergency, the Investigator will institute any medical procedures deemed appropriate. However, all such procedures must be promptly reported to the sponsor and the IRB/IEC.

ADVERSE EVENTS (AE)

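### The GAI change ratings have no stated comparator although baseline photographs exist, and photography is listed as an efficacy endpoint with no defined read-out and inconsistent view instructions

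*Combined protocol and SAP*

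**What the plan says.** **GAI.** Appendix II, Table 5 defines a four-level scale (0 to 3) running from no change to significant improvement, so each score is a judgement relative to an earlier state. Table 2 schedules an improvement assessment on this scale at the 4, 8 and 12 week follow-ups. It assigns investigator satisfaction and subject satisfaction to the separate satisfaction scale, Table 6. The Return Visits section differs: it has the investigator's satisfaction questionnaire, and the subject's improvement and satisfaction, all done on the GAI.

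**Photography as an endpoint.** The section Primary and Secondary Efficacy Endpoint opens with "Primary and secondary objectives will be measured using the next efficacy endpoints" and ends its list with "6. Photography". The synopsis carries the same list. Under Follow-up Visit Measurements the plan states: "Follow-up measurements for weight, circumference and digital images will be used for comparative measurements with their respective measurement at baseline". The Treatment Visit paragraph also uses photographs to document adverse events.

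**Views.** The Study Design Overview says "photography will be performed under visible light conditions of the front, right, left and back view". Appendix IV, under Abdomen, says "Three photographs should be taken at each specified time point" and then gives five bullets: front, plus 45° and 90° from each side.

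**Consistency over time.** The Baseline section asks for consistent camera and subject placement. Appendix IV asks for controlled subject positioning. The Return Visits section requires follow-up photographs to be taken as they were at baseline.

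**The concern.** A change rating needs a reference. If the rater has nothing in view but the present abdomen, the score depends on how well the earlier appearance is remembered, and at the last visit that is about four months back. This is a one-arm study in which subject and investigator both know that treatment was given. A vaguely remembered starting point leaves more room for expectation to fill the gap. The result matters to the report: subject improvement is part of a secondary objective, and the synopsis lists subject assessments among the data to be tested at alpha 0.05.

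The photographs could supply the reference, but the plan does not connect the two. Photography stands instead as an efficacy endpoint of its own, from which no result can be derived as written. Sites that follow different view instructions would also hold different image sets.

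**Working it through.** **1. Time from baseline to each GAI rating.** Inputs: treatments two weeks apart (synopsis); follow-ups 4, 8 and 12 weeks after the third treatment, each ±7 days (Return Visits); ±5 days for the second and third treatments (Table 3). I assume that the baseline photographs are taken on the day of the first treatment, which the plan prefers.

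The plan's own duration reproduces: 2 + 2 + 12 = 16 weeks. In days, the nominal interval is 28 + follow-up day. The range is ±(5 + 7) = ±12 days if the third-treatment window counts from baseline, and ±(5 + 5 + 7) = ±17 days if the two treatment windows accumulate.

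| Visit | Nominal | ±12 days | ±17 days |
|---|---|---|---|
| 4 wk FU | 28 + 28 = 56 d = 8 wk | 6.3 to 9.7 wk | 5.6 to 10.4 wk |
| 8 wk FU | 28 + 56 = 84 d = 12 wk | 10.3 to 13.7 wk | 9.6 to 14.4 wk |
| 12 wk FU | 28 + 84 = 112 d = 16 wk | 14.3 to 17.7 wk | 13.6 to 18.4 wk |

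**2. Comparator for the GAI.** Three places could state it. Table 2 gives timing and scale. Return Visits gives rater and scale. Appendix II gives the response levels. None mentions a reference image, and none forbids one.

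**3. Read-out for photography.** Six efficacy endpoints are listed. Set against the objectives:
- endpoints 1 to 3 (ultrasound, caliper, tape) serve the primary objective and secondary objectives 1 to 3;
- endpoints 4 and 5 (investigator satisfaction; subject improvement and satisfaction) serve secondary objectives 4 and 5;
- endpoint 6 (photography) serves no stated objective.

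Table 2 attaches a scale to pain, immediate response, satisfaction and improvement. For photographs it names only the images. The Statistical Methods row of the synopsis names no photographic variable.

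**4. Views.**

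| View | Study Design Overview | Appendix IV bullets |
|---|---|---|
| Front | yes | yes |
| Right | yes (angle not given) | 90° |
| Left | yes (angle not given) | 90° |
| 45° right, 45° left | no | yes |
| Back | yes | no |
| **Count** | **4** | **5 listed, 3 stated** |

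There are thus two lists and one count that fits neither. If the side views in the overview are read as the 90° views, the real disagreements are the back view and the two obliques.

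**The case against.** The strongest reply is that little depends on this. The primary endpoint is ultrasound fat thickness, no objective names photography, and no test is planned on images. The stated three above five explicit bullets looks like an editorial slip. All of that stands, and it keeps the point small.

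Several stronger readings are tempting, and the documents do not support them:

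- *The GAI is rated from memory.* The plan is silent; it neither requires nor excludes viewing the baseline images. The full questionnaires are not reproduced, and a figure between Tables 5 and 6 is not visible in the text available, so its content cannot be judged. Only an unspecified reference can be claimed.
- *The photographic endpoint is empty.* The images have stated uses, namely comparison with baseline and adverse-event documentation. What is missing is a method for the comparison.
- *Before-and-after sets will not match within a subject, because two arm poses are allowed.* Appendix IV does say "it is best to either cross them over each other in front of the chest or hold them up at a 90° angle". However, the Return Visits rule, the Baseline placement rule and the positioning rule in Appendix IV already tie follow-up images to the baseline procedure. The residual problem is uniformity between sites, of which there may be up to ten.
- *Every rating is 16 weeks from baseline.* That holds for the last visit only.

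A further objection is that photographs beside an unmasked rater do not remove expectation bias. That is correct, and the fix claims only to reduce recall error. It is also correct that a photograph-assisted GAI is still endpoint 5, so it should not be presented as a separate photographic result.

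**Conclusion.** The point holds as a modest, inexpensive improvement. The GAI is a change rating made nominally 8, 12 and 16 weeks after baseline with no stated comparator, so recall cannot be excluded even though suitable images will be on file. Photography carries the label of an efficacy endpoint without a rater, scale or variable. The view instructions give counts of 4, 3 and 5 that cannot all be followed.

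The effect of recall on the GAI scores cannot be sized from the documents, and I put no figure on it. The intervals assume that baseline coincides with the first treatment; with visit windows the last rating may fall anywhere from 13.6 to 18.4 weeks. The primary efficacy conclusion does not depend on any of this.

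One related inconsistency must be settled first: Return Visits gives the investigator the GAI, whereas Table 2 gives investigator satisfaction the Table 6 scale.

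**What to change.** 1. Reconcile Return Visits with Table 2 on whether the investigator completes the GAI or only the satisfaction scale. Then require each GAI rating to be made by the existing rater with that subject's baseline photographs displayed beside the same-visit photographs in the same views. State this in Return Visits and under Table 5.
2. Use a single view list in the Study Design Overview and Appendix IV, and make the stated number agree with it.
3. Move photography out of the efficacy endpoint lists (synopsis and main text) and describe it as supporting documentation for the GAI and for safety.

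The cost is protocol wording and a few minutes per follow-up visit; no new images or readers are needed. The downside is that ratings may shift compared with ratings made without images, so the procedure should be in force at all sites from the first follow-up visit. Expectation bias in unmasked raters remains and should be acknowledged when the GAI is reported.
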